Sample size calculations were performed using GLIMMMPSE Version 3.⁴³ Though a Bayesian model averaging approach will be used, sample size calculations using a non-Bayesian approach are applicable here because they correspond to the model that is believed to be most likely true *a priori*, and also because we plan to use uninformative priors on the parameters in the model, which makes our analyses comparable to the non-Bayesian approach that is used for sample size calculations. As we do not have pilot data to inform our sample size calculations for the NAS/non-NAS group, our sample size calculations are based on the group means by gender that were observed in the pilot study on “total puffs” and a standard deviation of 5.5.³¹ Given NAS smokers’ preexisting misperceptions about natural/organic cigarettes, we anticipate that group means will be more extreme in the NAS/non-NAS group.⁴⁴ Thus, the minimum sample size required for Aim 3 analyses should be sufficient to address the Aim 2 analyses. Assuming an intraclass correlation between repeated measurements of 0.5, 40 total subjects are needed to detect a significant interaction between gender and condition (natural/organic vs conventional/own brand) at 90% power and a significance level of 5%, while 99% power requires 68 subjects. Since these assumptions use information based on only 22 subjects in the pilot study, sample size calculations were also performed with an effect size 50% smaller and a

covariance matrix 50% larger than assumed: under these conditions, 90% power is achieved with 228 total subjects. Fewer subjects are needed to detect differences hypothesized in Aim 1 at each given power; for example, under the smallest effect size observed in the topography pilot data (which assumes a mean difference of 120ml with standard deviation 165ml), 120 subjects are needed to achieve 90% power under an effect size that is 50% smaller and covariance matrix that is 50% larger than assumed. Thus, we will enroll 125 participants per cigarette type (250 total, though we have budgeted for up to 300 participants to account for loss to follow up) to ensure at least 228 participants complete the full study. Our proposed sample size is adequate to detect a similar topography effect size to our pilot study, examine moderation by NAS preference and gender, and allow for adjustments to the significance level due to multiple comparisons.

Statistical analyses

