We will consider models that: 1) allow the effect of the condition (conventional, organic, and natural) to differ based on NAS-smoking status and gender (as hypothesized); 2) allow the effect of the condition to differ based only on NAS-smoking status; 3) allow the effect of the condition to differ based only on gender; and 4) do not allow the effect of the condition to differ based on NAS-smoking status or gender. We will also consider models that combine the effects of the natural and organic conditions, as we believe the effects of these two conditions could be similar for our outcomes. We will also consider in the model an effect for the own brand

condition (which may or not depend on NAS-smoking status and gender), period effects, random effects, and effects for other covariates that may be predictive of the outcome. Bayes factors will be used to determine if the effect of the condition depends on NAS-smoking status or gender, and if a combined effect (one effect vs two) should be used in the model for the natural and organic conditions.

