Preliminary analyses assume there are no carryover effects. However, sensitivity to this assumption will be examined by considering models that instead assume there are carryover effects (as described above); if there are carryover effects, then the effect of the condition also depends on the period (in addition to possibly gender and NAS-smoking status). For the main analyses that assume there are no carryover effects, we will use uninformative priors for all model parameters. Markov Chain Monte Carlo (MCMC) sampling will be used to estimate the posterior distribution of the model parameters; if there is a convergence issue for a parameter (e.g. if variance hyperparameters are on the boundary) or if model fit is a concern, we will instead consider weakly informative priors.⁵¹ When uninformative priors are used, results using a single candidate model with a Bayesian model averaging approach are equivalent to non-Bayesian, frequentist analyses (i.e. maximum likelihood estimation techniques).

To assess sensitivity of our choice of prior for the carryover effect, we will use a process similar to Grieve (1985).⁴⁸ To allow for a carryover effect, we will first use a Normal distribution with mean 0 and variance σ_{co}^2 as the prior for the carryover effects, and use an uninformative prior for σ_{co}^2 that ranges between 0 and ∞ . Next, we will let π be the prior odds of M_0 to M_1 , where M_0 is the model above without carryover effect and M_1 is the model with carryover

effect. We can then assess the impact of a range of prior belief in a carryover effect by repeating analyses for different values of π . The primary analyses assume there is no carryover effect, which corresponds to π equal to 1, while sensitivity analyses will assume there is a carryover effect, which corresponds to $0 \leq \pi < 1$.

Since MCMC methods will be used, the entire posterior distribution corresponding to the parameters of interest will be estimated and can be produced as figures. Figures may be overlaid to show how results are sensitive to our choice of π . Even though we will obtain the entire posterior distribution of our parameters, we will also calculate 95% credible intervals, which is an alternative way of presenting effect sizes corresponding to hypotheses H(1.1) – H(3.4). Credible intervals will also be used to conduct hypothesis testing (details on hypothesis testing are below). Below are the model outcomes that will be used to test each hypothesis:

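### The 90% moderation power at 228 completers applies to a 5% interaction contrast and its 95% credible interval, not to the Bayes-factor step that first decides whether moderation enters the model

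*Combined protocol and SAP*

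**What the plan says.** The Sample size calculations section starts from pilot means by gender. It states that "40 total subjects are needed to detect a significant interaction between gender and condition" "at 90% power and a significance level of 5%, while 99% power requires 68 subjects". It then repeats the calculation under pessimistic inputs, with half the effect and a "covariance matrix 50% larger than assumed", and reports that "under these conditions, 90% power is achieved with 228 total subjects". That figure sets the target of at least 228 completers and so the enrolment of 250. A non-Bayesian calculation is defended partly on the ground that uninformative priors will be used, "which makes our analyses comparable to the non-Bayesian approach that is used for sample size calculations".

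The Statistical analyses section gives a different rule for deciding on moderation: "Bayes factors will be used to determine if the effect of the condition depends on NAS-smoking status or gender". It places this choice first, before estimation by model averaging, and ends with one model per outcome. For the main analyses, "we will use uninformative priors for all model parameters". It claims equivalence with maximum likelihood only for a single candidate model.

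The Hypothesis testing section begins Aim 1 by determining whether the condition effect depends on gender and NAS status. That answer sets the number of Aim 1 intervals. H(2.1) to H(3.4) are then tested by whether stated 95% credible intervals exclude 0.

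The documents give no Bayes-factor threshold and no prior scale for the interaction terms. They do not say what happens to the Aim 2 and 3 intervals if the Bayes factor selects a model without the interaction.

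**The concern.** The power statement and the first moderation decision rest on different rules. With diffuse priors, a posterior interval from one fixed model behaves like a confidence interval, so frequentist power transfers to it. A Bayes factor also weighs how widely the prior spreads over effects that the data do not support. Widening the prior raises the observed interaction needed to favour the moderation model. The property cited as the reason for comparability is therefore the one that separates this step from a 5% test.

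What is at stake is how a negative result is read. If the Bayes factor returns no dependence on gender or NAS status, a reader will take that as a finding with a 10% false-negative rate in the planning scenario. The plan does not support that rate. If the selected model also governs Aims 2 and 3, the gender or NAS difference in condition effects is zero by construction in a model without the interaction, and its interval cannot exclude 0.

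**Working it through.** **Inputs from the Sample size calculations section.** 40 subjects for 90% power, 68 for 99%, 5% level; then effect × 0.5, covariance × 1.5, 228 subjects for 90%. The pilot means by gender are not given, so noncentrality per subject is calibrated from the stated sample sizes.

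**Step 1: reproduce 40, 68 and 228.** Use a noncentral F test with 1 numerator df, N − 2 error df and two-sided 5%.

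- 90% power at N = 40 requires noncentrality 0.2767 per subject.
- The same value gives 99.0% at N = 68.
- Halving the effect and raising the covariance by 50% multiplies noncentrality by 0.5² / 1.5 = 1/6. At N = 228 the total is 228 × 0.2767 / 6 = 10.51, whose square root is 3.24, and power is 89.8%.
- In reverse, setting 228 to exactly 90% gives 90.2% at 40 and 99.0% at 68. A one-sided test set to 90% at 228 gives only 98.7% at 68. Tests with 2 or 3 df already pass 99% at 66.

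The printed figures are correct for a two-sided, 1-df, 5% interaction test. In the large-sample form, noncentrality at 228 is 1.960 + 1.282 = 3.242.

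**Step 2: the credible-interval rule.** With flat priors and the interaction in the model, a 95% interval excludes 0 when |z| > 1.96. Power is Φ(3.242 − 1.960) = 90%, so the printed figure stands for this rule.

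**Step 3: the Bayes-factor rule.** For threshold k:

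- Unit-information (BIC) approximation: the interaction is selected when z² > ln(n) + 2 ln(k).
- Normal prior with SD τ: it is selected when z² > ((1 + r)/r)(ln(1 + r) + 2 ln k), where r = (τ/SE)². With 114 per group, SE = contrast-SD × √(2/114), so r = 57τ² with τ in contrast-SDs.

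Power is Φ(3.242 − critical z); the opposite tail is negligible. Example, BIC with n = 228 and k = 1: critical z = √ln 228 = √5.429 = 2.330, and Φ(0.912) = 0.819.

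| Prior for the interaction (assumed) | BF>1: critical z, power | BF>3: critical z, power |
|---|---|---|
| Normal, SD = the planned (halved) effect, 0.43 contrast-SD | 1.64, 95% | 2.25, 84% |
| Normal, SD = 2 × that effect, about 0.85 | 1.96, 90% | 2.47, 78% |
| BIC, n = 228 subjects | 2.33, 82% | 2.76, 68% |
| BIC, n = 912 observations (228 × 4) | 2.61, 74% | 3.00, 59% |
| Normal, SD = 10 contrast-SDs | 2.94, 62% | 3.29, 48% |
| Normal, SD = 100 contrast-SDs | 3.64, 34% | 3.93, 25% |

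Cauchy priors of scale 0.5 and 0.707, by numerical integration, give 91% and 89% at BF>1, and 79% and 76% at BF>3. As τ grows, ln(1 + 57τ²) grows without limit, so a flat prior gives no fixed power.

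**Step 4: the two steps in sequence.** For one contrast, if the Bayes-factor critical value exceeds 1.96, every result that passes it also has a 95% interval excluding 0. The power of Bayes factor then interval is then the Bayes-factor power in the table. If the interval is always computed from the interaction model, it is the 90% of Step 2.

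**The case against.** The strongest reply is that H(2.1) to H(3.4) are not tested by Bayes factors. The Hypothesis testing section defines a 95% credible interval for each and does not make them conditional on the model choice, whereas the Aim 1 contrasts are explicitly conditional. On that reading, about 90% is right for Aims 2 and 3. This stands, and it limits the point. A reader might infer that the moderation hypotheses are decided by the Bayes factor and are simply underpowered; the documents do not say so. The difficulty is that the Statistical analyses section chooses one model per outcome by Bayes factor before estimation and does not exempt these intervals.

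A reader might also conclude that true power is about 82% or less. The documents do not support that either. The 82% needs a unit-information prior, threshold 1, one df and n counted as subjects, none of which is stated, and a proper prior with SD up to about twice the planned effect keeps BF>1 at 90% or above. That scale is hard to call uninformative, but it is not excluded: the plan allows weakly informative priors if convergence or fit is poor.

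Three further limits are fair.

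- The calibrated contrast is natural/organic against conventional/own brand on total puffs. The Bayes factor compares somewhat different models on four other outcomes, so the table shows the pattern, not a forecast for each outcome.
- 228 is already the pessimistic case. Under BIC with BF>1, power at 228 is about 95% if only the effect is halved (3.242 × √1.5 = 3.97 against 2.33) and above 99.9% at the pilot effect.
- Aims 2 and 3 are secondary.

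**Conclusion.** The concern holds in limited form. The arithmetic is sound: 40, 68 and 228 all reproduce. The error is in carrying the 90% over to a step that does not have it. It is right for a two-sided 5% interaction contrast, and for a 95% credible interval from a model containing the interaction. It is unsupported for the Bayes-factor step. It reaches Aims 2 and 3 only if that step fixes their model, which is suggested but not stated.

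No single replacement figure can be drawn from the documents. In the planning scenario, the tabulated range at BF>1 runs from 95% (prior SD equal to the planned effect) through 82% (unit-information) and 62% (SD 10) to 34% (SD 100). At BF>3 the same priors give 84%, 68%, 48% and 25%. The more literally the priors are uninformative, the larger the loss. These figures assume one interaction contrast, normal approximations and the plan's own halved effect and inflated covariance.

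**What to change.** 1. In Sample size calculations, limit the comparability sentence to credible intervals, and label 90% at 228 as the power of the two-sided 95%-interval contrast.
2. In Hypothesis testing, state that the Aim 2 and 3 intervals are computed from the model with the interaction whatever the Bayes factor selects, so that the 90% applies to them. If that is not intended, restate the power by simulation for the full sequence of Bayes factor then interval.
3. In Statistical analyses, replace uninformative priors on the interaction terms, for the Bayes factor only, with a proper prior of stated scale. State the threshold, and report the power of that step at 228 beside the 90%.

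The sample size stays as it is. The cost is one simulation, a few sentences, and possibly a less favourable stated power for the Bayes-factor step.

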H_{3.2}: Compared to men, women’s average ratings of the “chemical aftertaste” of the cigarettes in the “natural” and “organic” conditions will be higher (e.g., closer towards the “less chemical aftertaste” side of the scale) relative to their average ratings of the cigarette in the “conventional” condition.

H_{3.3}: Compared to men, the difference in women’s total puff volume will be greater in the “natural” and “organic” conditions relative to their own brand than the difference in the “conventional” condition relative to their own brand.

H_{3.4}: Compared to men, women’s change in salivary aldehyde concentrations pre/post study cigarette(s) administration will be greater in the “natural” and “organic” conditions relative to their own brand than in the “conventional” condition relative to their own brand.

Recruitment. We will recruit 125 adult daily NAS smokers and 125 adult daily non-NAS smokers (250 total). Our goal is to recruit 50% women for each group. Participants will be recruited via public online postings (e.g., Craigslist), participant referrals, physical flyers, and other means as necessary. Recruitment documents will direct potential participants to answer questions in an online screening survey. The screener will be programmed to identify eligible individuals and inform others that they are not eligible, and will collect IP address so that the study team may identify individuals who attempt to qualify for the study by taking the screener multiple times. Study personnel will contact eligible individuals to confirm eligibility and schedule their baseline session.

Eligibility. Eligible subjects will be daily cigarette smokers who smoke at least 5 cigarettes/ day and have smoked that amount for at least the past six months; are between 21 and 65 years old; are not currently undergoing smoking cessation treatment or trying to quit; are able to communicate fluently in English (speaking, writing, and reading); and are capable of providing written informed consent, which includes compliance with the requirements and restrictions listed in human participant protections.

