Total puff volume: We will collect participants' puffing behavior using a topography instrument developed and manufactured at the American University of Beirut and calibrated across labs to determine participants' total inhalation volume. To use the topography device, the cigarette is placed in a sterilized mouthpiece, and the internal pressure transducer measures pressure changes that occur during inhalation. The pressure changes are amplified, digitized and sampled at 1000 Hz, then software converts the signal to airflow (ml/s) in real time (s), and from this provides number of puffs, puff volume, puff duration, maximum flow, and interpuff interval (time between puffs). The primary topography outcome is total puff volume due to its well-characterized responsiveness to changes in cigarette type.³⁹⁻⁴¹

Biomarkers and saliva sample collection procedures

The primary purpose of the biomarker analysis is to assess whether exposure to aldehydes and nicotine in cigarette smoke varies by descriptor condition. These markers could reflect smoking behavior changes (i.e., mouth holding and inhalation) which could not be captured by topography measurement (i.e., puffing). Saliva samples will be collected from the participants before and after each ad lib tobacco product use bout in Sessions 2-5. The research

staff will ask subjects to wash their mouth with clean water when collecting the ‘before session’ saliva sample. The “after session” samples will be collected just after the participant finishes their last puff. Saliva samples (approx. 3 mL) will be collected using a Salimetrics saliva collection kit (Salimetrics, Carlsbad, CA). Saliva samples will be shipped to DRI Reno campus and be stored at -40°C prior to analysis. Salivary aldehydes (formaldehyde and acetaldehyde) and nicotine are exposure biomarkers. We will measure the concentration of these biomarkers in the mouth, before they are metabolized by the body, and make within-person comparisons in concentrations by study descriptor conditions. In addition, nicotine metabolites (cotinine and trans-3'-hydroxycotinine) will be measured to confirm smoking abstinence.

Missing data

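### The moderation sample size is worked out on number of puffs, so adequacy for a gender interaction on total puff volume (H3.3, secondary) is not shown

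*Combined protocol and SAP*

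**What the plan says.** The Sample size calculations section states that the moderation sizes are "based on the group means by gender that were observed in the pilot study on" total puffs, with an SD of 5.5. It continues: "Assuming an intraclass correlation between repeated measurements of 0.5, 40 total subjects are needed to detect a significant interaction between gender and condition" at 90% power and a 5% level, with 68 for 99% power. Halving the effect and enlarging the covariance matrix by 50% raises the 90% figure to 228. The section names the contrast as the natural and organic conditions against the conventional and own brand conditions. It assumes NAS group means will be more extreme than the gender means, so Aim 2 is taken to be covered by the Aim 3 size. Enrolment of 250 is chosen so that at least 228 complete, and the sample is then called adequate for moderation by NAS preference and gender.

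The outcome elsewhere is different. The Total puff volume paragraph says "The primary topography outcome is total puff volume", and its device description "provides number of puffs, puff volume, puff duration, maximum flow, and interpuff interval (time between puffs" lists puff count and puff volume as separate outputs. H3.3 reads "Compared to men, the difference in women’s total puff volume will be greater in the “natural” and “organic” conditions relative to their own brand", compared with the conventional condition relative to own brand. The Statistical analyses section treats every outcome outside the four primary ones as exploratory.

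The only sample size in ml is for the Aim 1 main effect, "which assumes a mean difference of 120ml with standard deviation 165ml". It gives 120 subjects under the same conservative adjustment.

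**The concern.** An SD of 5.5 cannot describe a volume whose SD is given as 165 ml a few lines later, so the interaction was sized on a count. Number of puffs appears in none of the hypotheses H1.1 to H3.4. The stated 90% power for moderation therefore belongs to no hypothesis the plan tests, although it sets the size of the trial.

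The contrast may differ as well. The sizing contrast could mean two conditions averaged against two. Under Hypothesis testing, the gender contrasts are pairwise: organic minus conventional and natural minus conventional, men against women.

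What is at stake is how a null moderation result on volume will be read. For Aim 2, the Hypothesis testing section takes an interval containing zero as evidence for the null. Readers need to know what size of interaction the trial could have detected in the units of the outcome.

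**Working it through.** **Inputs from the plan.** SD 165 ml; ICC 0.5; covariance enlarged by 50%; 90% power; 5% level; 228 completers; a goal of 50% women, taken as 114 per gender.

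**Assumptions not in the plan.** Two-sided test; the same SD in men and women; no multiplicity adjustment.

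**Step 1: reproduce the plan's figure in ml (Aim 1).** The effect is 120/2 = 60 ml and the SD is 165 × √1.5 = 202.1 ml.

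n = ((1.960 + 1.282) × 202.1 / 60)² = 119.2, so 120 as stated (122 by the t distribution). Multiplying the SD itself by 1.5 would give 179, so the enlargement is on the variance. At ICC 0.5 the SD of a difference between two conditions equals the SD of one measurement, because √(2 × (1 − 0.5)) = 1. It therefore does not matter which of the two the 165 ml is.

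**Step 2: what can be checked of 40, 68 and 228.** The pilot gender means for number of puffs are not given, so these cannot be rebuilt from raw inputs. They are mutually consistent: in a two-group comparison of a within-person contrast (noncentral t, equal groups), an interaction of 1.06 contrast SDs gives 40 at 90% power, 68 at 99%, and 228 at 90% with the effect halved and the variance multiplied by 1.5. No stated number is wrong.

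**Step 3: which contrasts H3.3 uses.** The intervals for H3.3 take (organic − own brand) − (conventional − own brand) in each gender. Own brand cancels, leaving organic − conventional. Natural works the same way. These are pairwise contrasts.

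**Step 4: detectable interaction in ml at 228.** For contrast weights c, the contrast SD is 202.1 × √((1 − 0.5) × Σc²). The detectable interaction is 3.242 × contrast SD × √(4/228), and √(4/228) = 0.1325.

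| Contrast | Σc² | Contrast SD (ml) | 90% power for | Power at 60 ml |
|---|---|---|---|---|
| Pairwise, as tested for H3.3 | 2 | 202.1 | 87 ml | 61% |
| Natural and organic averaged vs conventional | 1.5 | 175.0 | 75 ml | 73% |
| Two conditions averaged vs two | 1 | 142.9 | 61 ml | 88% |

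Power at 60 ml is by the noncentral t with 226 df. The 60 ml is only a yardstick, namely the plan's halved Aim 1 effect.

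**Step 5: sensitivity.**
- Without the 50% enlargement (SD 165 ml), the pairwise figure is 3.242 × 165 × 0.1325 = 71 ml, and power for 60 ml is 78%.
- With 250 completers and the enlargement, the pairwise figure is 83 ml.
- If 165 ml is the SD of a single measurement, ICC 0.3 to 0.7 moves the pairwise figure at 228 from 103 to 67 ml.
- A 40:60 gender split gives 89 ml.

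**The case against.** The strongest reply is that nothing here shows the trial is too small. The plan gives no expected gender interaction in ml, and 60 ml is a benchmark borrowed from a deliberately halved main effect. Against the unhalved 120 ml, which the plan calls the smallest effect in its topography pilot data, 87 ml is 73%, and it already carries the enlarged covariance. This stands. A reader might infer that 228 is inadequate, or that the interaction needed is implausibly large; the documents support neither.

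Second, if the contrast in the Sample size calculations section is two conditions averaged against two, the detectable figure is 61 ml. The plan also allows natural and organic to be merged if Bayes factors favour it, which gives 75 ml. Both are fair, and so the 87 ml must be quoted with its contrast. It remains the figure for the pairwise intervals set out for H3.3.

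Third, a reader might extend the result to H2.3. That would be wrong: H2.3 compares conditions within NAS smokers. With 114 NAS smokers and SD 202.1 ml, 90% power needs 3.242 × 202.1/√114 = 61 ml, and power for 60 ml is about 88%.

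Fourth, it is tempting to convert the 1.06 SD interaction into ml. The result would be 1.06 × 165 = 175 ml or 1.06 × 116.7 = 124 ml, depending on the contrast. It would also require count and volume to share one standardised interaction, which the documents do not say.

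Finally, Aims 2 and 3 are secondary, and the Aim 1 size of 120 is well below 228. That limits the weight of the point but does not answer it, because the moderation figure is what sets enrolment.

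**Conclusion.** The point holds as a gap in justification. The moderation sizes rest on an outcome the plan treats as exploratory, and possibly on a contrast other than the one tested. Adequacy for moderation of total puff volume is therefore unshown, rather than disproved.

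On the plan's own ml inputs, the detectable interaction at 228 ranges from 61 to 87 ml by contrast, with 87 ml applying to the pairwise H3.3 intervals. These figures rest on ICC 0.5, the 50% larger covariance, equal gender groups with a common SD, a two-sided 5% level and no multiplicity adjustment; any adjustment that widens the intervals would raise them. The same arithmetic would apply to a NAS-by-condition interaction on volume with equal groups. The primary Aim 1 calculation is unaffected.

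**What to change.** Recompute power for the gender-by-condition interaction, and for NAS-by-condition, on total puff volume. Use the pilot's gender-by-condition means in ml, SD 165 ml and ICC 0.5, for the pairwise contrasts listed under Hypothesis testing, in both the base and the 50%/50% conservative scenarios. The plan says it has no pilot data by NAS status, so the NAS assumption should be stated in ml. Say whether the sizing contrast is pairwise or averaged, and whether the test is two-sided. Replace the puff-count figures with the detectable interaction in ml at 228 and 250 completers.

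This costs a recalculation and a few restated sentences, with no extra participants. The drawback is that the stated moderation power may turn out less favourable.
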